Controlled and predictable tooth movement with minimal damage to the teeth and their supporting structures can be obtained by using light continuous force which is ideal for orthodontic treatment. To be clinically efficient, this force should cause maximum tooth movement with minimum root resorption and pain (**Wang *et al.*, 2018; Azizi *et al.*, 2021**). A combination of excellent springiness, excellent strength, and a large range of action that produces a flat load deflection rate has made NiTi wires ideal archwires to be chosen at the initial stages of orthodontic treatment (**Kapila and Sachdeva, 1989; Sebastian *et al.*, 2019**). In order to provide clinical advantages, different elements have been added since the introduction of NiTi archwires into orthodontics. Copper is one of these elements that have been added to nickel-titanium, to lower the loading stress while providing relatively high unloading

stress, which can result in more effective orthodontic tooth movement (**Gil and Planell, 1999; Atik *et al.*, 2019**).

Multistranding of archwires has been successfully attempted with stainless steel wire to gain mechanical advantages such as increased flexibility and a reduced load deflection rate (**Rucker and Kusy, 2002; Sebastian, 2012**). The same principle was applied in case of superelastic NiTi, this results in introduction of Supercable, a seven-stranded round coaxial superelastic NiTi archwire which became commercially available in 1995. Laboratory tests seem to suggest that these wires exert only 36% to 70% of the force of solid NiTi wires (**Berger and Waram, 2007; Sebastian, 2012**). Full bracket engagement with extremely low unloading force delivery is possible with this Supercable wire because of its high superelastic properties (**Berger and Jeffrey, 2008; Modi *et al.*, 2020**).

Recently, Speed six-stranded coaxial tubular superelastic NiTi is introduced into the market. It has many advantages over single-stranded superelastic NiTi, such as shortening of treatment time, increased spring back, resistance to deformation, and it delivers low-force (**Joseph *et al.*, 2019**). It has an increased flexibility by a “hollow center” design to allow it to fold over on itself so it can be fully engaged in the severe malalignment, while applying only a portion of the force levels of conventional initial archwires (**Sebastian *et al.*, 2019**).

Manufacturers of archwires claim that some archwire is ideal for use in clinical orthodontics based on specific properties, determined by laboratory testing, the performance of these materials in vivo is much more important for orthodontists and their patients. Early clinical trials using new arch wire materials failed to demonstrate improved alignment and there are a number of factors that may be suggested to influence the performance of any given archwire clinically such as: type of wire and properties produced during manufacturing, size and type of brackets used,

interbracket distance, degree of initial malalignment of teeth and treatment duration may all effect the success of orthodontic treatment (**Wang *et al.*, 2018**).

Sebastian *et al.* (2019) reported in their study that there is no statistically significant difference between the alignment efficiency of coaxial tubular superelastic NiTi and single-stranded superelastic NiTi for relieving lower anterior crowding in extraction cases. In contrast, **Joseph *et al.* (2019)** concluded that coaxial tubular superelastic NiTi wires showed a significant effectiveness than single-stranded NiTi in reducing lower anterior crowding after 4, 8, and 12 weeks. This was supported by a systematic review and meta-analysis of experimental clinical evidence on initial aligning archwires and archwire sequences which revealed that a multistranded A_{act} NiTi archwires were significantly more efficient in terms of three dimensional (3D) contact point movement than its single-stranded analogs (**Papageorgiou *et al.*, 2014**).

Other studies concluded that both A-NiTi and Cu-NiTi archwires are equally effective for tooth alignment (**Atik *et al.*, 2019**; **Azizi *et al.*, 2021**).

The Cochrane review by **Wang *et al.* (2018)** revealed that there is a need for further randomized clinical trials (RCTs) to determine the best aligning archwire. Therefore, since there is no clinical study has been conducted until now to assess the alignment efficiency of superelastic coaxial tubular NiTi wire compared to Cu-NiTi wire, and since there is insufficient evidence to determine whether any of these archwire materials is superior to the other in terms of alignment rate, time to alignment, pain and root resorption. Hence, this RCT will be performed to compare between superelastic coaxial tubular NiTi wire and Cu-NiTi wire to assess these aspects in crowding cases.

Aim and Objectives

Aim

The aim of this study is to compare the effectiveness of using coaxial tubular superelastic nickel-titanium and copper-nickel-titanium archwires during the initial phase of orthodontic treatment.

Objectives

Primary Objective

To compare the difference in the amount of crowding relief of the mandibular incisors after 4, 8, 12 and 16 weeks from the start of treatment.

Secondary Objectives

1. To compare the amount of orthodontically-induced inflammatory root resorption (OIIRR) in the apical region of mandibular central incisors, after 16 weeks, between the two groups of archwires.
2. To compare the amount of pain perception between the two groups of archwires during the 1st week after each wire placement.

The *null hypothesis* is that “*there is no significant differences in the effectiveness of using coaxial tubular superelastic nickel-titanium and copper nickel-titanium archwires during the initial phase of orthodontic treatment*”.

Methodology

Study design

This will be a multicenter randomized clinical trial.

Settings

Different private clinics and general hospitals will allocate patients for this trial.

Subjects

Participants for this study will include any patient seeking fixed appliance orthodontic treatment according to the below criteria:

Inclusion Criteria:

1. Patients indicated for fixed appliance orthodontic treatment with 5-9 mm crowding of mandibular anterior teeth according to Little's irregularity index (LII).
2. Presence of all the mandibular permanent teeth, except the third molars.
3. Overbite and overjet that do not interfere with bracket placement on mandibular anterior teeth.
4. No history of trauma or root resorption in the mandibular incisors.

Exclusion Criteria:

1. Previous orthodontic treatment.
2. Less than 5 mm of mandibular incisors crowding (LII).
3. Severe crowding which requires treatment by extraction of premolars in the mandibular arch.
4. Blocked-out teeth that cannot be engaged with the aligning archwire.
5. Prior experience of periodontal disease and loss of attachment.

Sample Size

The sample size was calculated to detect a difference of 1.5 mm in the amount of crowding relief between the two treatment groups according to the data obtained from the study by **Nabbat and [name] (2020)**. This revealed that 13 patients in each trial arm will be sufficient to detect this clinical difference (Totals 26 patients). In order to account for dropouts, a total of 30 patients will be calculated.

Intervention

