All the participants will receive a standardized treatment protocol. At the day of bonding, 0.016-inch archwire will be placed for the TuNT group. Eight weeks later it will be replaced by the 0.018-inch archwire for another eight weeks. While, for the CuNT group, 0.014-inch archwire will be placed at the day of bonding and eight weeks later it will be replaced by the 0.018-inch archwire for another eight weeks. Archwires will be tied to the bracket by elastomeric modules. If there is any debonding during treatment, this should be dealt with as an emergency case and re-bonded within 24 hours, otherwise the case will be considered as dropout. Since this study will be performed during the initial phase of treatment, no deviation in the protocol of treatment will be accepted (such as adding additional archwire in the sequence or using power chain). A good-quality alginate impression for the lower arch should be taken pre-treatment and after 4, 8, 12 and 16 weeks and a stone study model is obtained. Periapical X-ray for the mandibular central incisors will be taken pre-treatment and after 16 weeks. The participants will be provided by a visual analog scale (0-10) to record their pain perception during the first week after each wire placement.

Data Collection and Measurements

The following data will be collected and measured during the course of this trial for both groups:

Type of measurement	Pre-treatment T0	After 4 weeks T1	After 8 weeks T2	After 12 weeks T3	After 16 weeks T4
Little's irregularity index	✓	✓	✓	✓	✓
Root resorption using the scoring index that was provided by Malmgren et al. (1982)	✓				✓

Pain perception using visual analog scale (0-10)	24 hours	2 nd day	3 rd day	4 th day	5 th day	6 th day	7 th day
--	----------	---------------------	---------------------	---------------------	---------------------	---------------------	---------------------

Study model which should be free from any discrepancy (such as bubbles) will be used to measure LII using a digital Vernier caliper to calculate the amount of mesial and distal contact displacement from the mesial contact surface of right mandibular canine to that on the other side, to the nearest 0.01 mm. The sum of these measurements represents the amount of LII (**Little, 1975**).

Root resorption will be assessed using the scoring index by **Malmgren et al. (1982)**:

- **Grade 0:** Absence of apical root resorption.
- **Grade 1:** Irregular apical root contour.

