- **Grade 2:** Minor apical root resorption, a small area of root loss amounting to less than 2 mm.
- **Grade 3:** Severe apical root resorption from 2 mm to one third of the original root length.
- **Grade 4:** Extreme apical root resorption exceeding one third of the original root length.

The participants will be asked to record their pain perception for the first seven days after placement of archwire using visual analog scale as shown below:

[figure not shown]

Figure 1: Flowchart of data collection and measurement during this RCT.

Timetable

Duty	Expected time
Patient identification and allocation	4 months
Intervention period	4 months
Data collection and analysis	1 month
Writing up the thesis	10 months (starting from the beginning of the trial)
Total expected time to finish	About 10 to 11 months

Stopping Roles

If there is a severe pain in one group that cannot be tolerated by the participants, the study should be terminated.

Budget and Funding

The study is self-funded.

Ethical Approval

The protocol will be submitted to ethics committee.

Data Management and Analysis

Data will be analyzed using the Statistical Package for Social Sciences for Windows, version 25.0 (SPSS Inc., Chicago, Illinois, USA). The following statistical analyses will be used:

Descriptive Statistics

These will include number, frequencies, percentages, mean, median, and standard deviation.

Reliability Statistics

Little's irregularity index: An intraclass correlation coefficient (ICC) will be used to test inter- and intra-examiner reliability of 10 study models measured twice with a four-week interval.

Root resorption: Weighted kappa test will be used to test inter-examiner and intra-examiner reliability of 10 periapical radiographs scored twice with a four-week interval.

Inferential Statistics

Homogeneity of variance between groups will be checked by Levene's test, while normality of data distribution will be checked by Shapiro Wilk test. Assuming that the data are normally distributed due to large sample size (≥ 30) according to the central limit theorem, the following tests will be used:

- *Independent samples t-test:* to test the difference in the amount of crowding between groups.
- *Wilcoxon signed-rank test and Mann-Whitney U test:* to compare the root resorption at T0 and T4 and within each group and between groups (categorical data).
- *Chi-square test:* to compare pain perception between groups.

The significance level will be set as $p < 0.05$

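### Crowding relief is capped by each patient's starting LII, so if alignment is nearly complete by weeks 12-16, an unadjusted comparison of relief there can make a faster wire look equal

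*Combined protocol and SAP*

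**What the plan says.** All of this is in the combined protocol and SAP.

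- **Primary Objective:** "To compare the difference in the amount of crowding relief of the mandibular incisors after 4, 8, 12 and 16 weeks". No visit is named as the primary one.
- **Inclusion Criteria:** entry requires an LII of 5-9 mm.
- **Data Collection and Measurements:** LII is built from contact displacements measured on the study model: "The sum of these measurements represents the amount of LII". Models are taken at T0 and at weeks 4, 8, 12 and 16 (T1-T4).
- **Sample Size:** "The sample size was calculated to detect a difference of 1.5 mm in the amount of crowding relief between the two treatment groups", giving 13 per arm and 30 in total after a dropout allowance. The visit, SD and power are not stated.
- **Inferential Statistics:** an independent-samples t-test is used "to test the difference in the amount of crowding between groups". No baseline covariate is mentioned, and the wording does not settle whether the tested variable is relief or LII at the visit.
- **Introduction:** the rationale lists alignment rate and time to alignment among the open questions. No objective, measurement or analysis addresses time to alignment, and no measure summarises the path from T0 to T4.

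**The concern.** A sum of displacements has a floor at 0, so a patient who starts at 6 mm can never show more than 6 mm of relief, whichever wire is used. Once both arms are close to aligned, relief is close to the starting LII. A comparison of relief then compares starting crowding, which randomisation makes equal on average. A faster wire would show its advantage early, and the gap in relief would shrink as the slower wire caught up.

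At stake is how late results are read. The null hypothesis concerns effectiveness in general, and the rationale is partly about speed. A non-significant difference at week 12 or 16 could be reported as equal effectiveness when the wires differ in how quickly they align the teeth.

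**Working it through.** **1. The plan's own figure.** With a 1.5 mm difference, 13 per arm and two-sided 0.05 (sidedness assumed), the normal approximation gives SD = 1.5 × √(13/2) / (z₀.₉₇₅ + z_power).

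- 80% power: 1.5 × 2.550 / (1.960 + 0.842) = 1.365 mm (1.31 mm with the t distribution).
- 90% power: 1.5 × 2.550 / (1.960 + 1.282) = 1.18 mm (1.13 mm with the t distribution).
- Dropout: 26 / (1 − 4/30) = 30.

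The figure cannot be reproduced exactly because SD and power are missing, but it is attainable. Nothing below shows that 13 per arm is wrong.

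**2. The bound.** Let B be the common mean T0 LII, and R_s and R_f the mean residual LII in the slower and faster arms at a visit. The difference in mean relief is (B − R_f) − (B − R_s) = R_s − R_f ≤ R_s, because R_f ≥ 0. It cannot reach 1.5 mm once R_s < 1.5 mm. That is relief in the slower arm above:

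- 5 − 1.5 = 3.5 mm (70%) from 5 mm;
- 7 − 1.5 = 5.5 mm (79%) from 7 mm;
- 9 − 1.5 = 7.5 mm (83%) from 9 mm.

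**3. How fast is fast enough?** Take 7 mm, the midpoint of the entry range, as an assumed mean. A constant rate needs 5.5/12 = 0.46 mm/week for the cap to bind at week 12, or 5.5/16 = 0.34 mm/week at week 16. Under exponential alignment the required rate is ln(7/1.5)/t: 0.128 per week at week 12 and 0.096 at week 16. These are half-times of ln 2/0.128 = 5.4 weeks and ln 2/0.096 = 7.2 weeks.

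**4. Power under an assumed time course.** Assumptions: LII(t) = L0·exp(−kt); L0 uniform on 5-9 mm (SD 4/√12 = 1.15 mm); log-SD of k 0.35; measurement SD 0.3 mm, with values below 0 set to 0; 13 per arm; one wire twice as fast.

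| Slower-arm half-time (weeks) | 3 | 4 | 6 | 8 |
|---|---|---|---|---|
| Week-16 difference in mean relief (mm) | 0.2 | 0.4 | 0.9 | 1.2 |
| Week-16 power, t-test on relief | 6% | 14% | 40% | 67% |
| Week-16 power, LII adjusted for T0 | 34% | 76% | 96% | 98% |
| Week-4 power, LII adjusted for T0 | 99% | 99% | 99% | 98% |
| Average LII over 0-16 weeks, adjusted for T0 | 99% | 99% | 99% | 99% |

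At week 4 the difference in mean relief is about 1.4-1.7 mm, and the unadjusted t-test on relief has about 87-96% power. With a 12-week half-time the week-16 difference is still 1.56 mm.

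**5. What causes the loss.** In rows two and three the wires and the visit are the same; only the treatment of T0 LII changes. At half-times of 6 and 8 weeks, adjustment removes nearly all of the loss. At 3 weeks it does not (34%), and there the floor itself dominates. If the planned t-test is on LII at the visit rather than on relief, the same simulation gives week-16 power within about two percentage points of the adjusted row. The late loss therefore belongs mainly to unadjusted relief, although the bound in step 2 applies to either variable.

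**6. A smaller effect.** With a 1.5-fold speed ratio and the same half-times, adjusted average LII has 72/74/76/75% power, adjusted week 4 has 71/72/70/66%, and adjusted week 8 has 64/70/73/72%. Adjusted week 16 runs from about 23% to 71%.

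**The case against.** The strongest reply is that the plan already looks where the effect would be. Weeks 4 and 8 are part of the same objective, and no rule makes week 16 decisive. A gap at week 4 that closes by week 16 is a fair description of a faster wire. This stands, and it limits the consequence: a verdict of equal effectiveness would require setting the early visits aside. Protection at week 8 is weaker if alignment is fast. With an assumed comparator rate of 0.2 per week and a 1.5-fold ratio, the t-test on relief has 39% power there.

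A second reply is that the cap may never bind. This also stands. The documents give no expected LII at any follow-up visit, and slow alignment leaves room for a 1.5 mm difference at week 16.

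A third is that average LII hardly beats an adjusted week-4 comparison and has its own dilution. In the 2-fold scenarios the arms differ in average LII by 0.74/0.95/1.20/1.29 mm, never 1.5 mm, so the sample-size target does not carry over. This rules it out as a cost-free replacement for the primary comparison. Its merit as a supporting summary is that it needs no advance knowledge of the time course.

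A reader might go further and infer that the curves are meant to converge, that the plan sets a 1.5 mm target for the late visits, or that the trial is bound to find the wires equal. The documents support none of these: no convergence is stated, the 1.5 mm is attached to no visit, and the early visits are analysed too.

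**Conclusion.** The point holds in conditional form. The bound is exact given equal mean baselines, which simple randomisation of about 30 patients delivers only on average. It follows from the LII definition and the 5-9 mm entry range. For a 7 mm mean start, a 1.5 mm difference is out of reach at week 16 if the slower arm's half-time is under about 7 weeks, and at week 12 if under about 5½ weeks.

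The power figures rest entirely on the assumed exponential course, the spread in rates, the measurement error and the 2-fold ratio. Within those assumptions, week-16 power on unadjusted relief is 6-67%, and adjustment for T0 LII raises it to 34-98%. Much of the loss is therefore avoidable by adjustment. What remains under fast alignment is a matter of interpretation: late non-significance says little about speed when little crowding is left. The finding does not show that the sample size is wrong or that the primary outcome must be replaced.

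**What to change.** In Inferential Statistics:

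1. Replace the unadjusted t-test on crowding with a comparison of LII adjusted for T0 LII, either as ANCOVA at each visit or as one longitudinal model over T1-T4.
2. Add, as a supporting summary of alignment speed, average LII over 0-16 weeks, adjusted for T0 LII. With equally spaced models the trapezoid average is (L₀/2 + L₄ + L₈ + L₁₂ + L₁₆/2)/4.
3. Report each arm's mean residual LII beside every visit difference.
4. State in advance that a non-significant difference at a visit where the slower arm's mean LII is below 1.5 mm will not be read as equal alignment speed.

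The cost is a little more analysis and no new data, since all five models are already planned. A rule is needed for patients with a missing model. The treatment protocol turns some debonding cases into dropouts, so incomplete paths should be expected; the longitudinal model can use the visits that exist. Average LII is less familiar to clinicians than millimetres of relief, so the visit means should stay in the report.

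### The primary objective gives four visits equal status under one null hypothesis, with no primary visit or decision rule, so the error rate of the trial's verdict is not controlled

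*Combined protocol and SAP*

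**What the plan says.** All references are to the combined protocol and SAP.

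- **Primary Objective:** compares "the amount of crowding relief of the mandibular incisors" between the arms "after 4, 8, 12 and 16 weeks from the start of treatment". No visit is given precedence. By contrast, the root resorption objective in the same section names one time point, 16 weeks.
- **Null hypothesis (Objectives):** there is one, that "there is no significant differences in the effectiveness of using coaxial tubular superelastic nickel-titanium and copper nickel-titanium archwires" in the initial treatment phase. It names no visit.
- **Sample Size:** "The sample size was calculated to detect a difference of 1.5 mm in the amount of crowding relief between the two treatment groups". The result is 13 per arm, 26 in total, raised to 30 for dropouts. No visit, SD or power is given.
- **Data Collection and Measurements:** LII is measured at T0 and at T1 to T4, so four post-baseline comparisons between the arms are available.
- **Inferential Statistics:** an independent samples t-test is listed "to test the difference in the amount of crowding between groups", and one line covers the level: "The significance level will be set as $p < 0.05". There is nothing on a primary visit, order of testing, adjustment or a combined model.

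**The concern.** Reporting four visits is a sound way to describe the time course of alignment. What is missing is the step from four results to one verdict on one null hypothesis. The natural reading of the plan is one unadjusted t-test per visit. Suppose the arms differ at week 4 and not at week 16, or the reverse. The plan does not say whether the null is then rejected, so that decision would be made with the results in view. The chance of a false claim depends on that decision: above 5% if one significant visit is enough, below 5% if all four are needed, and 5% only if one comparison was fixed beforehand.

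Two smaller gaps add to this. The objective and the sample size speak of relief, which is a change from T0, while the line for the test speaks of the amount of crowding, which can be read as the level at a visit. The 1.5 mm is tied to no visit, so the sample size cannot be matched to any one of the four tests.

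**Working it through.** **1. The plan's own figure.** The 13 per arm can be neither reproduced nor refuted, because SD and power are not stated. Working backwards with the normal approximation, n = 2·SD²·(z₀.₉₇₅ + z_power)² / δ², so SD = δ·√(n/2) / (z₀.₉₇₅ + z_power). For δ = 1.5 mm, n = 13 and 80% power: 1.5 × √6.5 / (1.960 + 0.842) = 1.37 mm. The exact t-test calculation gives 1.31 mm for 80% power and 1.13 mm for 90%. Nothing in the text links any of these SDs to a visit.

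**2. Reference points for four tests at 0.05 with no true difference.**

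- Independent tests, any visit counts: 1 − 0.95⁴ = 18.5%.
- Independent tests, all four required: 0.05⁴, which is practically zero.
- Perfectly correlated tests: 5% under either rule.

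Visits on the same patients, measured from the same baseline, lie between these extremes.

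**3. Correlated visits.** The documents give no between-visit correlations, so r = 0.7, 0.8 and 0.9 are assumed. Two patterns are used: the same correlation between all visits (exchangeable), and correlation that decays with distance between visits (AR(1)). The tests are pooled two-sample t-tests, two-sided 0.05 (the plan does not state sidedness), with 13 per arm. The results are simulated, with Monte Carlo error of about 0.1 percentage point.

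| Assumed correlation | Any visit counts | All four required |
|---|---|---|
| Exchangeable 0.7 | 13.3% | 0.5% |
| Exchangeable 0.8 | 11.7% | 0.9% |
| Exchangeable 0.9 | 9.6% | 1.8% |
| AR(1) 0.7 | 14.6% | 0.2% |
| AR(1) 0.8 | 12.9% | 0.5% |
| AR(1) 0.9 | 10.5% | 1.3% |
| One visit named beforehand | 5% | 5% |

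A third pattern treats relief as the running sum of independent 4-weekly gains. Then corr(i, j) = min(i, j)/√(i·j), for example 1/√4 = 0.50 between weeks 4 and 16. It gives 12.9% if any visit counts and 0.5% if all four are required. With 15 per arm the figures agree within 0.2 points.

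**4. Sensitivity to the assumed correlation.** The any-visit figure falls to about 8% at exchangeable r = 0.95 and rises to 18.0% at AR(1) r = 0.3. The low correlation is unlikely for repeated measurements from one baseline. The upper end of the 9-15% range needs the decaying pattern; the exchangeable pattern alone gives about 9-13%.

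**5. Price of adjusting instead of choosing.** Bonferroni over four visits (0.05/4 = 0.0125 each) would keep the any-visit rate at about 2.7-4.1% for r = 0.7-0.9. At 13 per arm, power at a single visit would fall from 80% to about 59% (SD 1.31 mm), or from 90% to about 75% (SD 1.13 mm). For a trial of this size, naming one comparison is cheaper.

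**The case against.** The tempting stronger reading is that this trial has a false-positive rate of 9-15%. The documents do not support it. They nowhere say that any significant visit rejects the null, and they do not say that all four must. Even the number of tests is an inference from the objective, since the analysis section gives one line. The certain finding is a missing decision rule; the percentages show what follows from one choice or the other.

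A reader might also infer that testing level instead of change would be an error. It would not: under randomisation both estimate the same between-arm difference, and each has a 5% error rate at a given visit. The wording in Inferential Statistics may be shorthand. Aligning it with the objective is a wording fix.

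Nor can a mismatch be claimed between the 1.5 mm and any visit. The figure comes from a cited study that is not part of the documents; one can say only that the visit is not stated.

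Finally, it can be said that this is an M.Sc. thesis with a descriptive aim, for which visit-by-visit reporting is customary. That is a fair defence of reporting all four visits. It does not cover the verdict, because the plan also sets a null hypothesis, a primary objective, a significance level and a sample size for a stated difference. That is a confirmatory frame, and it needs a rule.

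**Conclusion.** The point holds. Four visits share primary status under one null hypothesis, the only analysis is an independent t-test at 0.05, and no section says how the visits combine. The error rate of the verdict is therefore not controlled in either direction: about 9-15% if any visit suffices and about 0.2-1.8% if all four are required. The omission is plain from the text. The sizes rest on assumed correlations of 0.7-0.9, two-sided tests and 13 per arm. They cover crowding only; root resorption and pain, which could also be read under the effectiveness null, are not counted. The trial stays interpretable as a description of alignment over time, but its confirmatory conclusion is undefined until a rule is written. This should be corrected before analysis.

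**What to change.** Before analysis, add text to this effect:

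*The primary comparison is the between-arm difference in LII reduction from T0 to T4 (16 weeks), tested at two-sided 0.05. Weeks 4, 8 and 12 are secondary and are reported as between-arm differences with 95% confidence intervals.*

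T4 is one option. It is the only visit after the full two-wire sequence, since for each arm's first wire the Intervention Protocol says "Eight weeks later it will be replaced by the 0.018-inch archwire for another eight weeks". If the sponsor's main interest lies in early alignment, another single visit or one pre-specified contrast across visits serves equally well, provided it is justified and fixed beforehand.

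Two wording changes go with this:

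- In Inferential Statistics, describe the tested outcome as crowding relief, meaning change in LII from T0, to match the Primary Objective.
- In Sample Size, state which visit the 1.5 mm refers to.

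Cost: no extra patients, visits or measurements, provided the 1.5 mm and its SD apply to the chosen visit; if they do not, the sample size justification must be restated. The other visits lose confirmatory status. Choosing week 16 carries one further risk. Patients enter with "5-9 mm crowding of mandibular anterior teeth" and relief cannot exceed the starting value, so the arms may have converged by then. The documents do not show whether this will happen, and the sponsor should weigh it when choosing the visit.
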